8.8 Safety analyses

All analysis of safety data will use the Safety population.

All safety data will be summarized/analyzed by treatment group.

No statistical hypothesis testing will be performed.

Due to the COVID-19 situation and safety concerns over viral transmission, every investigational visit within the protocol is now be performed remotely (e.g. by phone) for all participants still active in the study by the investigational site staff. The investigational site will continue to monitor the health status of the participants by collecting information on general health status, Concomitant Medication and Adverse Events.

Page 41 of 69

M7.5 and M10.5 phone calls include a pre-diabetic questionnaire as recommended by the DSMB committee.

8.8.1 Adverse events

All AEs or treatment emergent adverse events (TEAEs) will be classified by Primary SOC and PT according to MedDRA Version 21.0 or higher.

AEs will be classified as pre-treatment AEs, TEAEs (treatment-emergent adverse events), or post-treatment AEs, defined as follows:

Pre-treatment AE: any AE that started before the first dose date of study drug intake (AE onset date < date of first study drug intake).

Treatment-emergent: An AE will be considered a TEAE if it starts on or after the first dose date of study drug up to the last dose date + 6 weeks (date of first randomized study medication intake \leq AE onset date \leq last dose date + 6 weeks).

Post-treatment AE: any AE that was newly developed after the last dose date + 6 weeks (AE onset date > last dose date + 6 weeks).

Details for imputing missing or partial start dates of adverse events are described in Section 7.1.4.

Summaries of the following will be presented.

An overall summary table with number and percentage of subjects and number of events for the following will be presented by treatment group and overall:

- All AEs (excluding pre and post treatment events)
- All TEAEs
- Treatment related TEAEs (AE will be defined as related if causality is either definitely, probably or potentially)
- Treatment related Serious TEAEs (AE will be defined as related if causality is either definitely, probably or potentially)
- TEAEs by maximum severity (if a subject has several AEs with the same SOC/PT. The AE will be included only once in the summary, this being the AE with maximum severity
- TEAEs leading to treatment discontinuation (action taken = 'Discontinued')
- Serious AEs/TEAEs
- TEAEs leading to death.
- Adverse events of special interest (AESI) (falls and injurious falls and orthostatic hypotension)
- Serious Adverse events of special interest (AESI) (falls and injurious falls and orthostatic hypotension

Version Final 2.0, Date: 04JUN2021

• Treatment related Adverse events of special interest (AESI) (falls and injurious falls and orthostatic hypotension)

Pre-treatment AEs and post-study AEs will be presented in the listings only.

The number and percentage of subjects with at least one AE and the number of AEs will be presented by SOC and PT for the categories above. Two AEs with the same PT and classified in the same category (pre-treatment AE, TEAE or post-study AE) will be considered as two different events when calculating the "number of events" in the summaries. The same rule will apply for SOCs summaries by SOC and PT will be presented in alphabetical order.

All information about AEs collected on the eCRF will be listed alongside the treatment, preferred term, and SOC. For Serious AEs, deaths, AEs related to the study treatment, TEAEs leading to treatment discontinuation and AESI, a separate listing will also be provided. In addition, where applicable, a separate flag to define the treatment period (pre-treatment/TEAE/post-treatment) will be included.

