8.3.4 TIME PERIOD AND FREQUENCY FOR EVENT ASSESSMENT AND FOLLOW-UP

The occurrence of an AE or SAE may come to the attention of study personnel during study visits, during interviews of a study participant presenting for medical care, or upon review by a study monitor. All AEs including local and systemic reactions not meeting the criteria for SAEs will be captured on the appropriate report form. Information to be collected includes event description, time of onset, clinician's assessment of severity, relationship to study product (assessed only by

those with the training and authority to make a diagnosis), and time of resolution/stabilization of the event. All AEs occurring while on study must be documented appropriately regardless of relationship. All AEs will be followed to adequate resolution.

A SAE follow-up includes a prompt blood sampling for PK analyses, if deemed applicable by the Investigator or by his/her staff. Any medical condition that is present at the time that the study participant is screened will be considered as baseline and not reported as an AE. However, if the study participant's condition deteriorates while performing any physical assessments at any time after signing the ICF (including the screening period), it will be recorded as an AE. Unanticipated problems (UPs) will be recorded in the data collection system throughout the study.

Changes in the severity of an AE will be documented to allow an assessment of the duration of the event at each level of severity. AEs characterized as intermittent require documentation of onset and duration of each episode.

The PI will record all reportable events with start dates occurring any time after informed consent is obtained until the last day of study participation. At each study visit, the investigator will inquire about the occurrence of AEs/SAEs since the last visit. Events will be followed for outcome information until resolution or stabilization.

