8.3.6 SERIOUS ADVERSE EVENT REPORTING

The study clinician will immediately report to the sponsor of any SAEs, whether or not considered study intervention related, including those listed in the protocol or investigator brochure, and must include an assessment of whether there is a reasonable possibility that the study intervention caused the event. Study endpoints that are SAEs (e.g. all-cause mortality) must be reported in accordance with the protocol unless there is evidence suggesting a causal relationship between the study intervention and the event (e.g. death from anaphylaxis). In that case, the investigator must immediately report the event to the sponsor.

All SAEs will be followed until satisfactory resolution or until the site investigator deems the event to be chronic or the participant is stable. Other supporting documentation of the event may be requested by the Data Coordinating Center (DCC)/study sponsor and should be provided as soon as possible.

The study sponsor will be responsible for notifying the FDA of any unexpected fatal or lifethreatening suspected adverse reaction as soon as possible, but in no case later than 7 calendar days after the sponsor's initial receipt of the information. In addition, the sponsor must notify the FDA and all participating investigators in an Investigational New Drug (IND) safety report of potential serious risks, from clinical trials or any other source, as soon as possible, but in no case later than 15 calendar days after the sponsor determines that the information qualifies for reporting.

Follow-up information on SAEs must also be reported by the investigator within the same time frames.

If a non-serious AE becomes serious, this and other relevant follow-up information must also be provided to within one day as described above. For a non-serious AE that becomes serious but which is not fatal or life-threatening, a complete clinical report should be received within 5 days.

The following variables will be recorded for each AE: verbatim AE description, time and date for AE start and stop, maximum intensity, seriousness, causality rating, whether or not the AE caused the patient to discontinue, and the outcome.

All SAEs have to be reported, whether or not considered causally related to the study procedures. All SAEs will be recorded in the eCRF. The investigator is responsible for informing the IEC/IRB of the SAE based on local requirements.

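### SAP 8.8.1 defines a treatment-emergent adverse event by onset date alone, so an event that starts before first dose and worsens on study drug is left out of the TEAE summaries by arm

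*SAP*

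**What the plan says.** SAP 8.8.1 places each AE in one of three periods by comparing dates. Pre-treatment means "any AE that started before the first dose date of study drug intake (AE onset date < date of first study drug intake". On the other side, "An AE will be considered a TEAE if it starts on or after the first dose date of study drug", with the window closing six weeks after the last dose. Neither definition mentions a later change in severity or seriousness. The section then states: "Pre-treatment AEs and post-study AEs will be presented in the listings only".

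The overall summary opens with a row labelled "All AEs (excluding pre and post treatment events". Most other rows are limited to TEAEs, including "TEAEs by maximum severity" and "TEAEs leading to death". Four rows are not limited by their labels: *Serious AEs/TEAEs*, and the rows for AESI, serious AESI and treatment-related AESI.

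On data collection, protocol 8.3.5 has AEs recorded from informed consent. Protocol 8.3.4 says: "Changes in the severity of an AE will be documented to allow an assessment of the duration of the event at each level of severity". Protocol 8.3.6 says: "If a non-serious AE becomes serious, this and other relevant follow-up information must also be provided". The variables that 8.3.6 lists for each AE include one start, one stop and a maximum intensity; no date of worsening is named. Protocol 8.3.5 also keeps AEs that occur before randomization out of the analysis, with no exception for later worsening.

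**The concern.** A drug cannot cause an event that began before its first dose, but it can aggravate one. Aggravation on treatment is the part of such an event that could differ between arms, and the onset-date rule removes it from the comparison. SAP 8.8 plans no safety hypothesis tests, so the descriptive summaries by arm are the AE comparison that readers of the study report will use.

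The point is relevant to this trial. Protocol 2.3.1 asks for special surveillance of orthostatic symptoms because of the putative mechanism, and 8.3.8 names falls and orthostatic hypotension as events of special interest. Functional tests are done in screening and on Day 0, all before the first dose, and 8.3.4 records as an AE a deterioration that happens during a physical assessment after consent. Pre-dose AEs can therefore be of the same kind as the events under special watch.

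**Working it through.** The plan gives no figure here, so the check is a trace of the rules.

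**Can the case arise?** Yes. AEs are collected from consent (protocol 8.3.5), screening lasts 1 to 8 weeks (synopsis), and treatment starts the day after randomization (protocol 6.1.2). Any AE starting in that interval, Day 0 included, has onset before first dose. Protocol 8.3.4 and 8.3.6 treat worsening as change within one AE, and neither document tells sites to open a new record with a new onset date.

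**Trace.** Take one continuous AE, mild in screening week −3, that becomes severe and serious in week 10 under the same record (illustrative).

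1. Onset is before first dose, so it is pre-treatment and fails the TEAE condition.
2. Its place in the eleven rows of the SAP 8.8.1 overall summary is:

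| Summary row | Outcome |
|---|---|
| All AEs | Out, excluded by name |
| All TEAEs | Out |
| Treatment-related TEAEs | Out |
| Treatment-related serious TEAEs | Out |
| TEAEs by maximum severity | Out |
| TEAEs leading to discontinuation | Out |
| TEAEs leading to death | Out |
| Serious AEs/TEAEs | Conflict |
| AESI | Conflict |
| Serious AESI | Conflict |
| Treatment-related AESI | Conflict |

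3. Seven rows exclude the event. In the other four, the label would admit it and the listings-only sentence would remove it. The event-counting rule later in 8.8.1 adds to the conflict: it speaks of counts in the summaries and names pre-treatment AEs among the categories counted.
4. The tables by system organ class and preferred term use the same categories. The COVID-19 classification tables in SAP 8.7.6 use nearly all of them. Both inherit the result.
5. The event does appear in the full AE listing and, where applicable, in the separate listings for serious AEs, deaths, related AEs and AESI, flagged pre-treatment.

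**Protocol against SAP.** Protocol 8.3.5 draws its line at randomization and the SAP at first dose, about one day later. An AE that starts on Day 0 after randomization is outside the protocol's exclusion but inside the SAP's. The SAP's list of changes from the protocol mentions neither this nor any worsening rule.

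**Size.** The documents give no rate. Purely as an assumption, let 5% to 20% of 231 participants have an AE starting before first dose and 5% to 20% of those worsen on drug, at any grade:

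- Low: 231 × 0.05 × 0.05 = 0.6 participants; per arm, 77 × 0.05 × 0.05 = 0.2.
- High: 231 × 0.20 × 0.20 = 9.2 participants; per arm, 77 × 0.20 × 0.20 = 3.1.

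**The case against.** Much can be said on the other side, and part of it stands.

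- **The events are not hidden.** A reader might infer that such an event reaches no table at all. The documents do not support that. The serious and AESI rows are ambiguous rather than empty. The listings for serious AEs, deaths and AESI show the event, and SAP 8.2 sorts listings by treatment group. Disposition (8.3), laboratory shift tables (8.8.2) and standing and sitting or lying blood pressure (8.8.3) are summarised by arm whatever the AE class, and the DSMB reviews safety data. What stands is that listings give no counts or percentages by arm, and that the seven rows above exclude the event without ambiguity.
- **Many worsenings escape the rule.** A reader might picture mild dizziness in screening that becomes orthostatic hypotension with hospitalisation on drug. That example is unsafe: orthostatic hypotension has its own definition in protocol 2.3.1 and could be entered as a new event with its own onset, which makes it a TEAE. Intermittent AEs have each episode's onset recorded (protocol 8.3.4), and a condition present at screening is baseline, not an AE. This stands, and it confines the point to one continuous AE kept under one record.
- **The SAP largely follows the protocol.** Protocol 8.3.5 excludes AEs occurring before randomization. True, but it is equally silent on later worsening. It shares the gap and must be amended or reconciled too.
- **The data may not support a correction.** Protocol 8.3.6 lists no date of worsening. Protocol 8.3.4 does require severity changes to be documented, but whether the eCRF holds their dates cannot be told from the documents. This stands and adds to the cost.

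**Conclusion.** The point holds in a limited form. Followed as written, SAP 8.8.1 miscounts one kind of event: a continuous AE that starts after consent and before first dose and then worsens, becomes serious or is fatal on drug. It is missing from the TEAE, treatment-related, maximum-severity, discontinuation and death summaries, and its place in the serious and AESI rows is undetermined. This is a stated rule that gives the wrong count, not an omitted detail.

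The number of participants affected is unknown and may be small. A reader might take from the illustrative range that one to three serious events per arm are lost. The documents do not support that: both rates are guesses, the range counts worsening of any grade, and its low end is well under one participant per arm. The serious or fatal share is unquantified and could be zero. The conclusion also assumes that sites do not enter each worsening as a new AE; an instruction to that effect outside these two documents would close the gap.

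**What to change.** Before unblinding:

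1. In SAP 8.8.1, define a TEAE as an AE that starts on or after first dose, or that started before first dose and increases in severity or becomes serious on or after first dose, in both cases up to six weeks after last dose. State that a fatal outcome in that window counts as worsening, since the severity scale in protocol 8.3.3.1 has no fatal grade.
2. Limit the listings-only sentence and the exclusion in the *All AEs* row to pre-treatment AEs that did not worsen. Apply the same rule to the serious and AESI rows and to the event-counting rule, so that one definition governs every table.
3. For these events, use the date of worsening for timing and the on-treatment severity in the maximum-severity table.
4. Align the rule with protocol 8.3.5 and enter it in the SAP's list of changes from the protocol.
5. Derive worsening from the severity changes documented under protocol 8.3.4. Confirm that the eCRF holds the date of each change and of becoming serious; if not, query the affected records.

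The cost is a short SAP amendment, one derivation, and queries on what are likely to be few records. No new assessment of participants is needed.

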7 STUDY INTERVENTION DISCONTINUATION AND PARTICIPANT DISCONTINUATION/WITHDRAWAL

7.1 DISCONTINUATION OF STUDY INTERVENTION

The Investigator should discontinue study intervention and specifically ensure that a participant stops taking the investigational drug if the bioanalytical results at Month 1 or Month 3 shows the following changes:

1. Confirmed 3-fold or greater elevations above the Upper Limits of Normal (ULN) of

These stopping rules for discontinuation are established based on

Discontinuation from investigational oral treatment does not mean discontinuation from the study, and remaining study procedures should be completed as indicated by the study protocol. If a clinically significant finding is identified (including, but not limited to, changes from baseline) after enrollment, the investigator or qualified designee will determine if any change in participant management is needed. Any new clinically relevant finding will be reported as an AE.

The data to be collected at the time of study intervention discontinuation will include the following:

- AE complete follow-up (if the treatment is stopped following an AE)
- Last investigational medication administration date and time

The physician can decide to re-introduce the investigational treatment if it was stopped because of a concomitant acute condition he/she considers unrelated to the treatment.

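### SAP 8.8.1: the All AEs row equals the TEAE row by definition, and events starting more than 6 weeks after last dose leave the death row and, on the natural reading, the other adverse-event tables

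*SAP*

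**What the plan says.** SAP 8.8.1 sets up three classes: "AEs will be classified as pre-treatment AEs, TEAEs (treatment-emergent adverse events), or post-treatment AEs, defined as follows". The middle class is defined by "An AE will be considered a TEAE if it starts on or after the first dose date of study drug up to the last dose", with a further 6 weeks allowed. The third is "any AE that was newly developed after the last dose date + 6 weeks". The first two rows of the overall summary are "All AEs (excluding pre and post treatment events") and all TEAEs.

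The death row is restricted to TEAEs. The serious-event row is labelled for both AEs and TEAEs. The special-interest rows (falls, injurious falls, orthostatic hypotension) carry no treatment-emergent label. The section then states: "Pre-treatment AEs and post-study AEs will be presented in the listings only". The term changes here from post-treatment to post-study. The next paragraphs of 8.8.1 use post-study as the name of the third class and then return to post-treatment for the listing flag.

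Protocol 7.1 says: "Discontinuation from investigational oral treatment does not mean discontinuation from the study, and remaining study procedures should be completed". Protocol 7.2 lets a participant continue after stopping drug. Protocol 8.3.4 says "All AEs occurring while on study must be documented appropriately regardless of relationship" and records events to the last day of participation.

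**The concern.** Two rows with different names should hold different events. SAP 8.7.6 also asks for all AEs and all TEAEs as separate COVID-period outputs, so the SAP treats them as distinct. As 8.8.1 defines them, they are not.

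The AE tables give numbers and percentages of subjects in the safety population, which is everyone randomized with any evidence of drug use. Someone who stops at Month 1 and stays is in that denominator throughout, but can count as a case only until 6 weeks after the last dose. No exposure-adjusted AE rate is planned. Early stopping can depend on treatment, because the laboratory rule in protocol 7.1 and adverse events in 7.2 can both trigger it. An arm with more early stopping then has less time in which to show an event, and its percentages fall for that reason alone.

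The protocol sets no such limit. Section 8.3.5 excludes only events before randomization from the analysis, and 9.4.5 promises AE tables with no cut-off after last dose. The SAP's list of changes from the protocol discloses a change to the safety population but not this window.

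**Working it through.** The plan states no figure on this point, so there is none to reproduce.

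**1. Row identity.** The three classes are defined by onset date alone: before first dose; from first dose to last dose + 6 weeks; after last dose + 6 weeks. They do not overlap and leave no gap. Hence all AEs − pre-treatment − post-treatment = TEAEs.

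**2. Time outside the window.** Let *s* be the week of last dose and *T* the week of the last AE contact.

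- Weeks outside the window = *T* − (*s* + 6); share of follow-up = (*T* − *s* − 6)/*T*.
- *s* = 4 and 12 are Month 1 and Month 3, the laboratory stopping points named in protocol 7.1; *s* = 20 shows a late stop.
- *T* = 26 + 6 = 32 (protocol synopsis: call 6 weeks after M6), or 39 + 6 = 45 (schedule of activities).
- As a sensitivity, *T* = 26 or 39 if AE collection ends at the end-of-intervention visit.

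| Plan, last AE contact | Stop week 4 | Stop week 12 | Stop week 20 |
|---|---|---|---|
| 26-week, T = 32 | 22/32 = 69% | 14/32 = 44% | 6/32 = 19% |
| 26-week, T = 26 | 16/26 = 62% | 8/26 = 31% | 0 |
| 39-week, T = 45 | 35/45 = 78% | 27/45 = 60% | 19/45 = 42% |
| 39-week, T = 39 | 29/39 = 74% | 21/39 = 54% | 13/39 = 33% |

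More than half of total follow-up is lost only if *s* < *T*/2 − 6, that is before week 10 (T = 32) or week 16.5 (T = 45). A participant who completes treatment loses nothing up to the 6-week call.

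**3. Illustrative effect on a percentage.** All inputs here are assumptions: the same constant hazard in both arms, on and off drug; 30% of participants with an event by week 32; a fraction *q* stopping at week *s*, all of whom stay to week 32.

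- Tabulated percentage = (1 − *q*) × 0.30 + *q* × [1 − 0.7^((*s*+6)/32)].
- Stop at week 4: in-window risk 1 − 0.7^(10/32) = 0.1055. Stop at week 12: 1 − 0.7^(18/32) = 0.1818.

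| Stopping, drug v placebo | All stops at week 4 | All stops at week 12 |
|---|---|---|
| 15% v 5% | 27.1% v 29.0% (1.9 points) | 28.2% v 29.4% (1.2 points) |
| 25% v 5% | 25.1% v 29.0% (3.9 points) | 27.0% v 29.4% (2.4 points) |

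For example, 0.85 × 0.30 + 0.15 × 0.1055 = 0.271 and 0.95 × 0.30 + 0.05 × 0.1055 = 0.290. With the same *q* and *s* in both arms the difference is zero.

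**The case against.** A TEAE window is a conventional choice, and this one is generous: with the single-dose half-life of 2.4 to 4.9 hours given in protocol 2.2, 6 weeks (1,008 hours) is more than 200 half-lives. No safety hypothesis is tested. Late events are not hidden: 8.8.1 requires separate listings of serious AEs, deaths and special-interest events with a treatment-period flag, and SAP 8.2 sorts listings by treatment group. In a trial of 231, late deaths can be counted from those listings. All of this stands, and it lowers the stakes. It does not make the two rows differ, and it does not give the reader a by-arm table of late events.

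The follow-up horizon is also open to question. The SAP flow chart times the last call 6 weeks after the end of treatment intake, which is where the window closes, and the schedule of activities allows the end-of-intervention visit to be brought forward on withdrawal. Protocol 8.3.5 ends AE recording at study completion or the end-of-study visit. Protocol 7.1 points the other way for those who stop drug and stay. The documents are mixed, hence the range of *T* above. Participants who leave the study altogether have no later follow-up to restore.

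A reader might infer that every safety table is cut. The documents do not support that: the laboratory, vital-sign, physical-examination and anthropometry summaries (SAP 8.8.2 to 8.8.5) run without this limit. A reader might also infer that a death or serious fall months after an early stop appears in no by-arm table. That is not established, because the serious and special-interest rows carry no TEAE label and the listing-only sentence says post-study. The usage later in 8.8.1 makes exclusion the likelier reading, but the text is ambiguous.

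**Conclusion.** The point holds for the adverse-event tables. The duplicate row and the TEAE-only death row follow directly from the SAP text. That later events are listed only rests on reading post-study as post-treatment, which is the natural reading but not the only one.

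It would be too strong to say that early stoppers lose most of their follow-up. That is so for a Month 1 stop on every horizon considered, but a Month 3 stop on the 26-week plan loses under half (44% or 31%).

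The effect on the results cannot be sized, because the documents do not say how many participants stop early and stay, or in which arm. The difference of roughly 1 to 4 points shows what assumed unequal stopping could do; it is not a forecast. It would favour whichever arm stops more often. This is a reporting gap worth closing because closing it is cheap; it does not undermine the safety analysis as a whole.

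**What to change.** In SAP 8.8.1:

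- Redefine the All AEs row as onset from first dose to the end of study participation, whatever the time since last dose.
- On that basis, tabulate by arm all AEs, serious AEs, all deaths and the special-interest events. Keep the TEAE tables unchanged beside them.
- State for each serious, special-interest and death row which window it uses, and apply the same definitions to the COVID-period outputs in 8.7.6.
- Use one term, post-treatment or post-study, throughout.
- Report person-time per arm for the TEAE window. The treatment-duration summary in 8.6.1 does not show the time at risk for a tabulated event.

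The cost is SAP wording and a second run of existing table programs; no new data are needed. The downside is that events long after the last dose dilute drug-related effects, which is why both windows should be shown.
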